For low-risk infants, the caregiver is adherent if the caregiver introduces peanut by 12 months of age. For high-risk infants, the caregiver is adherent if the clinician's testing indicates the introduction of peanut and the caregiver introduced peanut products by 7 months of age and continued feeding at least 6g over ≥ 3 feedings per week as reported around the infant's 1st birthday or the clinician's testing indicates avoidance of peanut and the caregiver does not introduce peanut products as reported around the infant's 1st birthday. For high-risk infants, the caregiver is partially adherent if the pediatric clinician and/or allergist's testing supports the introduction of peanut, and the caregiver introduces peanut products but does not do so by 6 months of age or does not continue feedings with at least 6 gm of peanut protein or over ≥ 3 feedings per week as reported around the infant's 1st birthday.

Figure 6. Caregiver Adherence

High Risk

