- A caregiver is adherent if the pediatric clinician and/or allergist's testing supports the introduction of peanut, and the caregiver introduces peanut products by 7 months of age and continues feedings with at least 6 g of peanut protein over ≥ 3 feedings per week as reported around the infant's 1st birthday ..
- A caregiver is adherent if the pediatric clinician and allergist's testing supports the avoidance of peanut and the caregiver does not introduce peanut products as reported around the infant's 1st birthday.
- A caregiver is *partially adherent* if the pediatric clinician and/or allergist's testing supports the introduction of peanut, and the caregiver introduces peanut products but does not do so by 6 months of age or does not continue feedings with at least 6 gm of peanut protein or over ≥ 3 feedings per week as reported around the infant's 1st birthday.
- A caregiver is non-adherent if the pediatric clinician and/or allergist's testing supports the avoidance of peanut, and the caregiver introduces peanut products as reported around the infant's 1st birthday.

The primary analysis of the exploratory endpoint will be repeated in the EEDI2 sample including pediatric clinician adherence, allergist adherence (high-risk only) and two-way interactions with each other and intervention group, as fixed effects predictors.

The primary analysis of the exploratory endpoint will be repeated in the EEDI2 sample by combining adherence and partial adherence and comparing partial and non-adherence.

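### High-risk caregiver adherence: avoidance is credited only on two test sources where the other rules accept one, and no written rule covers supported introduction that never happens

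*Combined protocol and SAP*

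**What the plan says.** Section 13.4.5 gives four rules for high-risk infants.

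- Adherent by introduction: "A caregiver is adherent if the pediatric clinician and/or allergist's testing supports the introduction of peanut, and the caregiver introduces peanut products by 7 months", with continued feeding at the stated amount and frequency.
- Adherent by avoidance: clinician *and* allergist "testing supports the avoidance of peanut and the caregiver does not introduce peanut products".
- Partially adherent: clinician and/or allergist "testing supports the introduction of peanut, and the caregiver introduces peanut products but does not do so by 6 months of age", or feeding is not continued as stated.
- Non-adherent: "A caregiver is non-adherent if the pediatric clinician and/or allergist's testing supports the avoidance of peanut, and the caregiver introduces peanut products".

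The same section restricts the high-risk analysis to infants with clinician and/or allergist test data, treats the outcome as yes/no, and groups partial with non-adherent in the main analysis. It then repeats the analysis with adherent and partial merged, and with partial compared against non-adherent.

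Section 3.5 states the avoidance route with one source: "the clinician's testing indicates avoidance of peanut and the caregiver does not introduce peanut products as reported around the infant's 1st birthday". Section 13.2 restates the introduction endpoints using 7 months for both full and partial adherence. Sections 3.5 and 13.4.5 use 7 months for full adherence and 6 months for partial.

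**The concern.** Two features of the written rules do not fit together.

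First, the avoidance rule is the only one of the four that joins the two test sources with a plain *and*. Single-source infants are explicitly in the analysis. For them, acting against the test result is scored as non-adherent, but acting in line with it cannot be scored as adherent.

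Second, when testing supports introduction, both available rules (adherent and partial) require that peanut was introduced. The only non-adherent rule concerns avoidance. A caregiver who never introduces peanut despite supportive testing meets none of the four. The low-risk rules in Section 13.4.5 do cover non-introduction, so this looks like an omission.

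At stake is the meaning of the exploratory endpoint, and of the exploratory peanut-allergy model in Section 13.4.4 that uses caregiver adherence as a predictor. If caregivers who avoid on allergist results are coded non-adherent, infants whose results point towards allergy are moved into the non-adherent group.

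**Working it through.** No sample-size or power figure bears on this point, so the check is to apply the four rules literally to every pattern.

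**Inputs (Section 13.4.5).** Clinician testing: none, supports introduction, supports avoidance. Allergist testing: the same three. Timing of introduction: never, by 6 months, between 6 and 7 months, after 7 months. Continued feeding, if peanut was introduced: met or not met.

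**Number of patterns.** There are 3 × 3 = 9 test pairs. Remove the pair with no testing (not in the analysis) and the two with opposite results (considered below): 9 − 1 − 2 = 6. Each pair has 1 never-introduced pattern plus 3 timings × 2 feeding states: 1 + 6 = 7. Total: 6 × 7 = 42.

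**Patterns that do not fall in exactly one category.**

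| Testing supports | Source | Caregiver | Category under Section 13.4.5 |
|---|---|---|---|
| Avoidance | Clinician only | Never introduces | None |
| Avoidance | Allergist only | Never introduces | None |
| Introduction | Clinician only | Never introduces | None |
| Introduction | Allergist only | Never introduces | None |
| Introduction | Both | Never introduces | None |
| Introduction | Clinician only, allergist only, or both (3 patterns) | Introduces between 6 and 7 months, feeding continued | Adherent and partially adherent |

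So 2 + 3 = 5 patterns have no category, 3 have two, and 42 − 5 − 3 = 34 have exactly one. These are counts of patterns, not of infants.

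**Single-source avoidance.** If peanut is introduced, every such pattern is non-adherent, as intended. If it is not introduced, no rule applies. Avoidance is adherent only when both sources support it.

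**Is allergist-only testing a real route?** Yes. In Section 13.4.2 the first way for the pediatric clinician to be adherent is referral without ordering sIgE, which leaves only the allergist's testing. Section 13.4.5 ties an allergist's avoidance recommendation to a large skin prick result or a failed feeding or challenge. The clinician-only case is less clear: in Section 13.4.2 a positive clinician sIgE leads to referral, and the plan does not say when clinician testing alone supports avoidance.

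**Repeat analyses.** On the written rules, every partially adherent infant had testing that supported introduction and every non-adherent infant had testing that supported avoidance. Comparing the two groups therefore compares test results as much as caregiver behaviour.

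**Opposite results.** If one source supports introduction and the other avoidance, a caregiver who introduces by 7 months and continues feeding meets both the adherent-by-introduction and the non-adherent rule, because each accepts either source. No precedence is stated.

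**The case against.** The strongest reply is that the main analysis does not need every case listed. Caregiver adherence is yes/no and is analysed in the same manner as the primary endpoint, for which Section 13.4.2 codes cases that miss the adherence criteria as non-adherent. That sentence is written for pediatric clinician adherence only, but even without it a caregiver who meets neither adherent rule is naturally a no. This largely stands for never-introducers. A reader might infer that they are simply unscored; for the main analysis the documents do not support that. The same default does not help the avoidance rule: it would code caregivers who avoided in line with a single test source as non-adherent, against Section 3.5.

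It is also fair to say that the plain *and* is probably a slip for *and/or*, and that *clinician* is used loosely elsewhere (Section 13.2). That explains the text but leaves the programmer with a literal rule that misclassifies. Section 3.5 refers to Figure 6 for the pathways, and the appendices list a caregiver pathway in Figure 8. Neither was available for this review; they may draw the missing branches, in which case the written rules should be made to match.

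Three stronger readings are tempting. One is that every infant with single-source avoidance testing is mis-scored; caregivers who introduce are classified as intended. Another is a shift of so many percentage points; the share of infants concerned is not in the documents, so any such figure only restates an assumed share. The third is bias between arms because the intervention changes testing. The order set in Section 6.1.1 supports both sIgE and referral, so neither the direction nor the existence of a difference in single-source testing can be established.

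**Conclusion.** The point holds for the written rules. The avoidance rule in Section 13.4.5 conflicts with the other three rules, with the section's own analysis set and with Section 3.5. Taken literally, it denies adherence to caregivers who avoid in line with single-source testing, chiefly allergist-only testing. The never-introduced gap is real in the text, but its main harm is to the repeat comparison of partial with non-adherence.

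The size in infants cannot be given: the documents state neither the mix of test sources nor the caregiver behaviour by test result. The conclusion assumes a literal reading and that Figures 6 and 8 do not override the text. The endpoint is exploratory. The primary endpoint and the main secondary analysis do not use it, so this is a minor point, though one that yields a wrong score if programmed as written.

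**What to change.** Reconcile Sections 3.5, 13.2 and 13.4.5 with one another and with Figures 6 and 8:

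1. Use the same test-source wording in all four high-risk rules, and say what counts as clinician testing that supports avoidance.
2. List supported introduction that never happens as an explicit category, and say whether the default in Section 13.4.2 applies to caregivers.
3. State how opposite clinician and allergist results are scored.
4. Reconcile the 6- and 7-month cut-offs so that no infant meets two rules.

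The aim is exactly one category for each tested infant. Aligning the test-source wording alone would not achieve this, because the overlap and the conflicting results would remain. Which clinical rule or cut-off applies is for the trial team; no view is taken here.

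The cost is a wording change to the protocol and SAP. Section 3.5 already lists test results and whether peanut was introduced among the data elements, so no new data are needed. The change should be made before outcomes are seen by arm, so that the scoring is not chosen after the fact.

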13.4.6 Descriptive Analyses

The number and percent of infants in all infant analysis samples will be tabulated by high- and low-risk group. Number and percent of infants for whom EHR data is obtained at each visit in the 4-month through 30-month data collection period will be summarized. Number and percent of infants who are lost to followup from each analysis sample will also be

summarized. Number and percent of pediatric clinicians and caregivers responding to each survey will be summarized.

The disposition of all pediatric clinicians treating infants in any infant sample will be summarized in tables and listed. The numbers and percent of treating pediatric clinicians consenting to participate in the study, withdrawing consent from study participation, and who treated infants throughout the entire study data collection, will be presented. Any information regarding reasons for pediatric clinician withdrawal of consent will be summarized and listed.

Summary descriptive statistics for demographics and baseline characteristics will be reported for all infant analysis samples and will be compared across samples to check for consistency. Variables to be summarized include age, race, ethnicity, and sex, as well as all components included in the assessment of high- or low-risk status.

Two types of outcomes will be monitored for all children in the infant analysis sample based on EHR data and caregiver surveys. First, the number of infants who react to first exposure to peanut will be reported. Second, the number of infants who have been fed peanut more than once and report a reaction after the first exposure.

Responses to all questions in the practice site, pediatric clinician characteristics questionnaires will be summarized overall and by trial arm.

Protocol deviations will be listed by practice with information such as type of deviation, severity of the deviation (major or non-major), date of occurrence, and the reason for the deviation. Protocol deviations will be summarized in tabular format by type of deviation.

Number and percent of pediatric clinicians utilizing individual iREACH prompts will be summarized to describe overall utilization of the iREACH intervention.

13.5 Interim Analyses

Not applicable.

13.5.1 Interim Analysis of Efficacy Data

Not applicable.

13.5.2 Interim Analysis of Safety Data

Not applicable.

13.5.3 Futility Analysis

Not applicable.

13.6 Statistical Hypotheses

Primary hypotheses: In each of the high-risk and low-risk strata, the primary endpoint analysis performs a test of superiority to assess whether the proportion of infants whose pediatric clinician is adherent to PPA Guidelines is different in the intervention arm compared to the control arm. A multiplicity adjustment will not be applied to the primary analysis because high and low-risk children represent independent risk strata where pediatric clinicians must take different steps to achieve adherence.

Null hypothesis: $P(\text{intervention group}) = P(\text{control group})$ where P denotes the proportion adherent.

Alternative hypothesis: $P(\text{intervention group}) \neq P(\text{control group})$

13.7 Sample Size Considerations

Power has been computed for primary and exploratory binary adherence outcomes and secondary peanut allergy outcomes. In order to compute power, six quantities have been specified: the type 1 error rate, the number of practice sites, the number of patients expected per practice site, the within cluster correlation, the average proportion adherent (or peanut allergic) over all practice sites and intervention arms, and the difference in proportion adherent (or peanut allergic) between the intervention and control arms. Calculations assume a type 1 error of 0.05. In this study, investigators can control the number of practice sites invited to participate in the study but cannot control the number of infants assessed at each practice site. Since deployment of the intervention and data collection are through the EHR, inclusion of additional practice sites does not require significant additional budget. Therefore, the choice of number of practice sites is based primarily on the number expected to participate and not on budgetary or statistical power concerns. We estimate that at minimum 30 clinics will participate. Using a preliminary EHR data pull, we estimate being able to assess on average 17 high-risk and 333 low-risk per clinic in 18 months for a total sample size of approximately 500 high-risk and 10,000 low-risk infants.

Since investigators cannot control the number of infants assessed, power calculations describe the differences between intervention arms in study outcomes that are detectable with 80% power for our given study sample sizes, rather than the sample sizes needed to be able to detect given differences between intervention arms in study outcomes.

Statistical power for primary and exploratory adherence outcomes: We assume a within cluster correlation of 0.07 for the pediatric clinician adherence outcomes, estimated from a preliminary EHR data pull. Similar studies have assumed lower correlations in the range of 0.001-0.01^{39,40} however, so we expect this estimate to be conservative. To further be conservative, we assume the average proportion adherent over all practice sites and intervention to be 0.50. These and the previously described assumptions and sample sizes allow us to detect with >80% power an absolute difference in proportions of adherence of $\geq 18\%$ in high-risk infants and $\geq 14\%$ in low-risk infants.

Statistical power for secondary peanut allergy outcome: We assume a within cluster correlation of 0.02 for the peanut allergy outcome, estimated from a preliminary EHR data pull on general food allergy. Peanut allergy prevalence data referenced earlier in this document provide estimates of the incidence of peanut allergy at age 2 of 13.8% for high-risk infants and 1.5% in low-risk infants. In high-risk infants, these and the previously described assumptions and sample sizes allow us to detect with >80% power an absolute difference in proportions with peanut allergy of 8.2% in high-risk infants (intervention and control arm proportions 5.4% and 13.8%). In low-risk infants, we can detect an absolute difference in proportions with peanut allergy of 0.98% (intervention and control arm proportions 0.11% and 1.50%). In high-risk infants, the LEAP study showed a 14% absolute difference in proportions with peanut allergy contrasting early introduction of peanut to avoidance. Compared to this, we are powered to detect smaller reductions in peanut allergy that might be expected with a CDS intervention.

14. Identification and Access to Source Data, Monitoring Plan

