| Primary Endpoint(s) | 
 Percent of infants at low risk for peanut allergy whose pediatric clinicians adhered to the guidelines. Percent of infants at high risk for peanut allergy whose pediatric clinicians adhered to the guidelines. |
| Secondary Endpoint(s) | 
 Percent of infants at low risk for peanut allergy who developed peanut allergy by age 2.5. Percent of infants at high risk for peanut allergy who developed peanut allergy by age 2.5. 
(Exploratory Objectives)
 
 Allergist adherence to the PPA Guidelines Barriers/facilitators for PPA Guideline adherence among pediatric clinicians and caregivers. Caregiver adherence to PPA Guidelines (peanut product introduction and feeding frequency). |
| Accrual Objective | Pediatric clinicians: 200; High-risk infants: 500; Low-risk infants: 10,000; Caregivers: 10,500 |
| Study Duration | 51 months for practices, maximum 23 months for pediatric clinicians, maximum 26 months for infants and caregivers |
| Treatment Description | The iREACH intervention consists of A) an education module on the PPA Guidelines and the research on which the guidelines were based; B) an EHR-integrated CDS tool in the 4- and 6-month WCC templates to support pediatric clinician decision-making around 1) proper triage of infants into peanut allergy risk categories, 2) allergy testing and interpretation and/or allergist referral for high-risk infants, and 3) caregiver counseling on peanut introduction including educational materials for families; and C) follow-up prompts in the 9-and 12-month WCC templates guiding pediatric |

| | |
|---------------------------|--|
| | clinicians to ask caregivers about inclusion of peanut products in their child's diet. |

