13.4 Analysis Plan

13.4.1 Analysis Populations.

Primary EHR data infant (PEDI) sample: All infants meeting inclusion/exclusion criteria for whom EHR data has been obtained at a 4-month or 6-month WCC in order to assess the primary endpoint of pediatric clinician adherence. Data regarding characteristics of the treating pediatric clinician are not required for an infant to be included in this population.

Secondary EHR data infant (SEDI) samples with pediatric clinician characteristics obtained: All infants meeting inclusion/exclusion criteria for whom EHR data has been obtained at a 4-month or 6-month WCC in order to assess the primary endpoint of pediatric clinician adherence and whose pediatric clinician has consented and completed the characteristics questionnaire information. In addition to characteristics obtained through the characteristics questionnaire information, data on completion of pre-study training for pediatric clinicians in the intervention arm will also be captured.

Exploratory EHR data infant (EEDI) samples

- With allergist adherence obtained (EEDI1): All high-risk infants meeting eligibility criteria who are referred to an allergist for testing and for whom data are obtained regarding the testing that was conducted, the outcome of the allergist testing and the recommendation provided by the allergist as to early introduction of peanut-containing food.
- With caregiver adherence obtained (EEDI2): All infants whose caregivers complete the FOABF and Caregiver Account of Clinician Peanut Recommendations, Testing and Introduction surveys at 12 and/or 24 months.

Pediatric clinician sample: All pediatric clinicians within the intervention group meeting consent and eligibility criteria who complete baseline and at least one follow-up knowledge, attitudes, or barriers and facilitators survey. Those clinicians in the control group will complete one follow-up knowledge, attitudes, or barriers and facilitators survey.

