13.4.5 Analyses of Exploratory Endpoint(s)

All analyses will be provided separately for high- and low-risk groups as noted. The entire infant sample of both risk groups will also be analyzed together where noted. Analyses will be treated as exploratory and hypothesis- generating, so no formal correction for multiple testing will be applied.

Allergist adherence will be analyzed with generalized linear mixed models for high-risk infants in the EEDI1 sample in the same manner as the primary pediatric clinician endpoint with infants as the unit of analysis. The allergist adherence endpoint will be determined as follows:

An allergist is adherent if:

- The allergist recommends introduction following a sIgE test ≤ 0.35 , a skin prick test 0-2mm, a successful supervised feeding or a successful oral graded food challenge.
- The allergist recommends avoidance and continued monitoring after a skin prick test ≥ 8 mm or a failed supervised feeding or oral graded food challenge.

An allergist is non-adherent if:

- The allergist fails to recommend introduction following a sIgE test ≤ 0.35 , a skin prick test 0-2mm, a successful supervised feeding or a successful oral graded food challenge.
- The allergist recommends introduction following a skin prick test 3-7mm without performing a supervised feeding or oral graded food challenge.
- The allergist recommends introduction following a skin prick test of ≥ 8 mm.

Caregiver adherence (yes/no) will be analyzed with generalized linear mixed models in the EEDI2 sample in the same manner as the primary pediatric clinician endpoint with infants as the unit of analysis. Only high risk infants with data on clinician and/or allergist testing will be used in the analysis of caregiver adherence. For the high risk infants in the primary analysis of the exploratory endpoint, partial caregiver adherence (as defined below) will be grouped with non-adherence. The caregiver adherence endpoint will be determined as follows:

For low-risk infants:

- A caregiver is adherent if the caregiver introduces peanut by 12 months of age, regardless of the pediatric clinician's recommendation.
- A caregiver is non-adherent if the caregiver does not introduce peanut by 12 months of age, regardless of the pediatric clinician's recommendation.

For high-risk infants:

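### The high-risk 18-point power statement in section 13.7 does not carry over to exploratory allergist and caregiver adherence, which use only subsets of the high-risk infants

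*Combined protocol and SAP*

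**What the plan says.** Section 13.7 opens by saying: "Power has been computed for primary and exploratory binary adherence outcomes and secondary peanut allergy outcomes". The adherence paragraph, labelled "Statistical power for primary and exploratory adherence outcomes", then gives more than 80% power for differences of 18 points (high-risk) and 14 points (low-risk). It relies on sample sizes set out just before it: on average 17 high-risk and 333 low-risk infants per clinic, about 500 and 10,000 in all. The exploratory outcomes get no sample size of their own.

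The analysis sections define smaller sets for those outcomes.

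- **Allergist adherence** (sections 13.4.1 and 13.4.5) uses EEDI1: "All high-risk infants meeting eligibility criteria who are referred to an allergist for testing", and for whom the testing, its outcome and the allergist's recommendation were obtained.
- **Caregiver adherence** uses EEDI2, infants whose caregivers completed the surveys. Section 13.4.5 narrows the high-risk part further: "Only high risk infants with data on clinician and/or allergist testing will be used in the analysis of caregiver adherence".

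The synopsis lists as accrual objective "Low-risk infants: 10,000; Caregivers: 10,500", beside 500 high-risk infants. Section 8.1 lets caregivers opt out of contact or refuse linkage of the survey to the child's record. Section 11.2 treats them as lost after five failed contacts.

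**The concern.** A power figure belongs to the set of infants that will be analysed. Here one figure, computed for every high-risk infant, is attached to outcomes that can be measured only in some of them.

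The restriction follows from the plan's own definitions. Under section 13.4.2, a high-risk infant who is neither tested nor referred counts as non-adherent, as does one with a positive test and no referral. Neither has the referral that EEDI1 requires. An infant with a negative test and a recommendation to introduce peanut counts as adherent without any referral, and so need not enter EEDI1 either.

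What is at stake is interpretation. A reader who takes section 13.7 at face value could treat a non-significant high-risk exploratory result as evidence against an 18-point effect, when the analysis may have had a much lower chance of finding one.

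**Working it through.** **Inputs**

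- Practices: "We estimate that at minimum 30 clinics will participate" (section 13.7), randomized 1:1 (section 13.3), so k = 15 per arm.
- Infants per practice: m = 17 high-risk and 333 low-risk (section 13.7).
- Within-cluster correlation: ICC = 0.07, stated for pediatric clinician adherence (section 13.7).
- Mean proportion adherent: 0.50 (section 13.7).
- Error rate: "Calculations assume a type 1 error of 0.05". Taken as two-sided, because section 13.6 tests whether the proportion "is different in the intervention arm compared to the control arm".
- Fraction f of infants analysed: not in the documents, so assumed and varied. The same f is used in both arms, with equal cluster sizes.

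**Formulas**

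- Design effect DE = 1 + (m − 1) × ICC; effective n per arm = k × m / DE.
- p1 = 0.50 − d/2 and p2 = 0.50 + d/2.
- SE0 = √(0.5/n); SE1 = √([p1(1 − p1) + p2(1 − p2)]/n).
- Power = Φ((d − 1.96 × SE0)/SE1).

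**Step 1: reproduce the plan's figures**

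- High-risk: DE = 1 + 16 × 0.07 = 2.12; n = 15 × 17/2.12 = 120.3. At d = 0.18, SE0 = 0.0645 and SE1 = 0.0634, so power = Φ((0.18 − 0.1264)/0.0634) = 0.801. Detectable difference at 80% power: 18.0 points.
- Low-risk: DE = 1 + 332 × 0.07 = 24.24; n = 15 × 333/24.24 = 206.1. At d = 0.14, SE0 = 0.0493 and SE1 = 0.0488, so power = 0.814. Detectable difference: 13.8 points.

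Both match section 13.7, and both use the full clusters. The high-risk figure has no slack: with 500/30 = 16.7 infants per practice, power is already 0.798.

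**Step 2: high-risk subsets, m = 17f, ICC 0.07, 30 practices**

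| f (assumed) | m | DE | effective n per arm | power at 18 points | detectable difference, points |
|---|---|---|---|---|---|
| 100% | 17 | 2.12 | 120.3 | 0.801 | 18.0 |
| 75% | 12.75 | 1.82 | 104.9 | 0.745 | 19.2 |
| 50% | 8.5 | 1.53 | 83.6 | 0.646 | 21.5 |
| 30% | 5.1 | 1.29 | 59.4 | 0.501 | 25.4 |
| 20% | 3.4 | 1.17 | 43.7 | 0.389 | 29.6 |

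Using SE1 in place of SE0 raises power by about one percentage point and gives detectable differences of 19.0, 21.2, 24.9 and 28.7 points in the last four rows.

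**Step 3: sensitivity of the high-risk result at 18 points**

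- ICC 0.001–0.01 (the range section 13.7 cites from similar studies), 30 practices: power about 0.80–0.83 at f = 50% and 0.59–0.62 at f = 30%.
- All 37 practices (18.5 per arm), ICC 0.07: power about 0.74 at f = 50% and 0.59 at f = 30%.

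**Step 4: low-risk caregiver adherence, m = 333f, ICC 0.07, 30 practices**

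- f = 50%: power at 14 points 0.799, detectable difference 14.0 points.
- f = 30%: power 0.779, detectable difference 14.3–14.4 points.

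With clusters this large the correlation dominates, so losing infants costs little.

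**The case against.** The strongest reply is that little depends on this. Section 13.4.5 calls these analyses exploratory and hypothesis-generating. Section 13.6 sets formal hypotheses for the primary endpoint only. Section 13.7 says the number of practices was not chosen mainly on power. The plan also has no rule for reading a null exploratory result. All of that stands. It limits the weight of the point, but it does not make the power statement true for these outcomes.

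The size is also conditional. No document gives f. The ICC of 0.07 is stated for pediatric clinicians only, and section 4.1 expects one allergist to see infants from both arms, so it may not carry over. Thirty practices is a conservative floor, since section 13.1 reports 37 recruited. At low ICCs the 18-point figure roughly survives with half of the infants; at 30% it fails in every scenario shown.

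A reader might infer more than the documents support:

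- **That the arithmetic is wrong or the primary endpoint underpowered.** Neither follows; both stated figures reproduce.
- **That low-risk caregiver adherence is similarly affected.** Step 4 shows that it is not.
- **That a 100% survey response was built into the calculation.** The 10,500 caregivers equal 500 + 10,000, which is optimistic, but section 13.7 does not use that figure.
- **That any gap in allergist data removes an infant.** Section 3.5 has an expert panel adjudicate missing elements. The panel cannot restore infants who were never referred.

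**Conclusion.** The point holds for two outcomes: high-risk allergist adherence and high-risk caregiver adherence. Section 13.7 claims more than 80% power at 18 points for them on the strength of infants whom their own definitions exclude. At the plan's ICC and 30 practices there is no margin to absorb any loss.

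How far power falls cannot be read from the documents. Steps 2 and 3 are illustrations that rest on an assumed fraction, an ICC borrowed from another outcome, equal clusters and a normal approximation. This is an error of scope in the power statement, worth correcting but confined to exploratory analyses.

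**What to change.** In section 13.7, limit the 18-point statement to the primary endpoint, and amend the opening sentence and the paragraph label to match.

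For high-risk EEDI1 and EEDI2, either tabulate detectable differences over stated referral, testing and response fractions and a stated range of ICCs, as in steps 2 and 3, or say that these exploratory analyses are not powered.

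For low-risk caregiver adherence, keep the 14-point figure and note the response rate down to which it still holds: about 50% at ICC 0.07.

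The cost is a wording change in the analysis plan and a less favourable figure for the exploratory outcomes. Design, sample size and primary analysis stay as they are.
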